8.3.3. Study Stopping Criteria

If, at any time during the study, any of the criteria listed below are reported in subjects treated with setrusumab, DMC will be notified to review if any alteration of study procedures is warranted:

- Two or more subjects with any serious TEAE with a severity ≥ Grade 3 (according to the Common Terminology Criteria for Adverse Events [CTCAE] version 5.0) that is assessed as related to study drug or study procedures by the Investigator or Ultragenyx
- One or more subjects with a hypersensitivity reaction that is considered Grade 4 or higher and assessed as related to study drug by the Investigator or Ultragenyx

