5.5. Risk Minimization

[figure not shown]
This study has been carefully designed to minimize potential risks to subjects.

The study includes measures to monitor patients with an aim to minimize potential risks of setrusumab based on safety data from previous clinical studies with setrusumab as well as product class information from other anti-sclerostin antibodies.

The following potential risks will require reporting to permit processing as AESI for the study (refer to Appendix 4 for details on safety reporting).

Measures to minimize risk and monitor for AESIs are listed below.

Additional measures to monitor for other potential risks are listed below.

In addition to the above, the incidence, seriousness, severity, duration, and outcome of all potential risks will be regularly monitored throughout the study and follow up will be performed to obtain complete information on all reported events to enable a thorough medical assessment.

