8.2. Exclusion Criteria

Individuals who meet any of the following exclusion criteria will not be eligible to enroll in UX143-CL203:

- 1. Known hypersensitivity to setrusumab or its excipients that, in the judgment of the Investigator, places the subject at increased risk for adverse effects.
- 2. Presence or history of any condition that, in the view of the Investigator, would interfere with participation, pose undue risk, or would confound interpretation of results.
- 3. Pregnant or breastfeeding or planning to become pregnant (self or partner) at any time during the study
- 4. Willing to discontinue bisphosphonate use at least 3 months prior to the Retreatment Screening Visit (if applicable). Once enrolled in UX143-CL203, individuals who meet any of the following exclusion criteria will not be eligible to participate in the Retreatment Period:
- 5. Concurrent participation in any study that is examining the safety and efficacy of any investigational product or investigational medical device that alters bone health during the Retreatment and Extension Periods, per discretion of the Investigator in consultation with the Medical Monitor.
- 6. Presence or history of any condition that, in the view of the Investigator, would interfere with participation, pose undue risk, or would confound interpretation of results.
- 7. Calcium levels outside the normal range. If the subject's calcium level is not within the normal range, decision to retest should be made in conjunction with the Medical Monitor.
- 8. GFR ≤ 29 mL/min. If the subject's GFR is ≤ 29 mL/min, decision to retest should be made in conjunction with the Medical Monitor.
- 9. History of skeletal malignancies or bone metastases at any time
- 10. History of neural foraminal stenosis (except if due to scoliosis)

11. History of myocardial infarction, angina pectoris, ischemic stroke or transient ischemic attack

- a. Investigators should consider whether the potential benefits of treatment outweigh the potential risks in patients with other cardiovascular risk factors such as hypertension, hyperlipidemia, familial hyperlipidemia, family history of premature ischemic cardiovascular disease, smoking, diabetes mellitus, and metabolic syndrome. Suggested criteria and references for evaluation of risk factors will be provided in the Study Reference Manual.

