10.6.1. Adverse Events of Special Interest

AESIs for this study include the potential risks of ischemic cardiovascular events, infusion reactions and hypersensitivity, and neurologic sequelae associated with bone overgrowth. Medical Dictionary for Regulatory Activities (MedDRA) search strategies will be specified for AESIs in the Statistical Analysis Plan, and include standardized MedDRA queries, if available.

AESI will be collected from the time the subject signs the ICF and through the safety follow-up period and should be reported within 24 hours of site Investigator, designee or site personnel's knowledge of the event as outlined in Table 11.

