An overdose is defined as a known deliberate or accidental administration of investigational drug, to or by a study subject, at a dose above that which is assigned to that individual subject according to the study protocol. All cases of overdose (with or without associated AEs) will be documented in the CRF. **Assessment of Severity**

The severity or intensity of an AE refers to the extent to which an AE affects the patient's daily activities. The severity of all AEs will be graded using the Common Terminology Criteria for Adverse Events (CTCAE) version 5.0, published on 27 November 2017.

If an AE cannot be graded using the CTCAE criteria, it should be graded using the following definitions:

• Mild (Grade 1): Asymptomatic or mild symptoms; clinical or diagnostic observations only; intervention not indicated.

- Moderate (Grade 2): Minimal, local or noninvasive intervention indicated; limiting ageappropriate instrumental activities of daily living (ADL). Note: Instrumental ADL refer to preparing meals, shopping for groceries or clothes, using the telephone, managing money, etc.
- Severe (Grade 3): Medically significant but not immediately life-threatening; hospitalization or prolongation of hospitalization indicated; disabling; limiting self care ADL. Note: Self care ADL refer to bathing, dressing and undressing, feeding self, using the toilet, taking medications and not bedridden.
- Life-threatening (Grade 4): Urgent intervention indicated.
- Death (Grade 5): Death related to AE.

Note: The term "severe" is often used to describe the intensity (severity) of a specific event (as in mild, moderate, or severe myocardial infarction); the event itself, however, may be of relatively minor medical significance (such as severe headache). This is not the same as "serious" which is based on subject/event outcome or action criteria and is usually associated with events that pose a threat to a subject's life or functioning. Seriousness (not severity) serves as a guide for defining regulatory reporting obligations.

Assessment of Causality

The Investigator will make a causality assessment about the relationship of each AE to study drug. Treatment-related conditions must be distinguished from disease-related conditions.

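### Section 8.3.3 requires DMC notification after one related Grade 4 hypersensitivity reaction, but after a related death from any other cause only if a second subject also qualifies

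*Combined protocol and SAP*

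**What the plan says.** Under section 8.3.3, if either of two criteria is reported in subjects treated with setrusumab, the "DMC will be notified to review if any alteration of study procedures is warranted".

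- **Two-subject criterion:** "Two or more subjects with any serious TEAE with a severity ≥ Grade 3", where the Investigator or the sponsor judges the event related to study drug or study procedures. It covers any serious TEAE, so the two subjects need not have the same kind of event.
- **One-subject criterion:** "One or more subjects with a hypersensitivity reaction that is considered Grade 4 or higher", where the Investigator or the sponsor judges the reaction related to study drug.

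Appendix 3 lists death among the criteria for a serious adverse event, and its severity scale gives "Death (Grade 5): Death related to AE".

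Other visible text on the flow of safety information:

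- Section 11.5 has the DMC review study data, including cardiovascular events and other AESIs, at a frequency set in its charter. It may recommend continuing, stopping or modifying the study.
- Appendix 4, Table 11 sends SAEs and AESIs to Electronic Data Capture, with the sponsor as back-up, within 24 hours.
- Appendix 4 sends SUSARs to regulators, IRBs/IECs and investigators; fatal or life-threatening ones go within seven calendar days. Notices about urgent safety measures and major safety findings go to the same three groups.
- Section 5.5 states that "Measures to minimize risk and monitor for AESIs are listed below", but the list does not appear in the public text.

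**The concern.** The protocol already accepts that a single event can justify asking the DMC whether the study should change. It then reserves that route for hypersensitivity. A related death from any other cause is serious and Grade 5, yet if it comes first it is one subject short of the two-subject criterion. A related Grade 4 hypersensitivity reaction that the subject survives meets 8.3.3 at once. No visible passage gives a reason for this order.

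At stake is whether the protocol itself obliges someone to bring a first related death to the independent committee when it happens, rather than at the next scheduled review. Retreatment is open-label and single-arm (section 7.1), so no concurrent untreated group helps the sponsor interpret one event. The dose may be up to 40 mg/kg, whereas the highest ASTEROID dose was 20 mg/kg. Independent advice on a first related death is reasonable in that setting.

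**Working it through.** **Reading the rule.** The plan gives no operating characteristic for 8.3.3, so there is no stated figure to reproduce. Three cases, each as the first qualifying event in the study:

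| Event in one subject, judged related | Two-subject criterion | One-subject criterion | 8.3.3 met? |
|---|---|---|---|
| Grade 4 hypersensitivity, survived | not met alone | met | yes |
| Fatal hypersensitivity (Grade 5) | not met alone | met | yes |
| Death from any other cause (Grade 5) | one of two | does not apply | no |

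If another subject already has a related serious TEAE of Grade 3 or higher, the death is the second qualifying subject and 8.3.3 is met.

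**Other routes.** In the visible text, Appendix 4 names Electronic Data Capture, the sponsor, regulators, IRBs/IECs and investigators as recipients, but not the DMC. Section 11.5 does bring data to the DMC, on a charter-defined schedule. Section 8.3.3 is therefore the only visible event-driven route.

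**Illustration of size.** The rates are assumptions; the documents give none.

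- n = 112, the enrolment maximum (section 7.1.2), with all subjects treated.
- p = 0.25% per subject for a related death not due to hypersensitivity.
- q = 0.5%, 1% or 2% per subject for any other related serious Grade 3+ event in the pooled criterion.
- Subjects are independent and event order is exchangeable. Grade 4+ hypersensitivity, which notifies alone, is left out of q; including it would lower the first two results below.

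The chance that a subject qualifies at all is r = p + q − pq.

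1. Chance that at least one such death occurs: 1 − (1 − 0.0025)^112 = 0.244.
2. Chance that a death occurs and is the first qualifying event, so that it does not meet 8.3.3: (p/r) × [1 − (1 − r)^112].
3. Chance that a death occurs and 8.3.3 is never met (one death, no other qualifying subject): 112 × p × (1 − r)^111 = 0.28 × (1 − r)^111.

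| q | r | Death is first | Death, 8.3.3 never met |
|---|---|---|---|
| 0.5% | 0.00749 | 0.334 × 0.569 = 0.190 | 0.28 × 0.434 = 0.122 |
| 1% | 0.01248 | 0.200 × 0.755 = 0.151 | 0.28 × 0.248 = 0.070 |
| 2% | 0.02245 | 0.111 × 0.921 = 0.103 | 0.28 × 0.080 = 0.023 |

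With an assumed 80 treated subjects, the same formulas give 0.15, 0.13 and 0.09 (first) and 0.11, 0.07 and 0.03 (never met).

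4. Expected single-death notifications under the fix: n × p = 112 × 0.0025 = 0.28. This is an upper bound on the extra ones, because some deaths would meet 8.3.3 anyway.

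These figures describe whether 8.3.3 is met. They do not measure whether or when the DMC learns of a death.

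**The case against.** The best defence is that the consequence lies in a document nobody outside can read. Section 11.5 leaves meeting frequency and scope to the charter, which may already require immediate notice of any death; the list announced in section 5.5 may bear on this too. Text that is not visible is not a gap in the plan. Nor is 8.3.3 the DMC's only basis for acting, since 11.5 gives it a standing remit to recommend changes or termination, and nothing stops the sponsor from informing it sooner. **This stands.** A reader might infer that the DMC would not hear of a related death, or would hear too late. The documents do not support that.

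A second defence is that the two-subject criterion is already sensitive: it pools event types, includes procedure-related events and accepts either party's causality judgment. This also stands, and it is why the figures fall as q rises. It does not help when the death comes first.

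A third is that unequal thresholds may be deliberate. The protocol does not say so, but severe hypersensitivity is tied closely to infusion and may recur at the next monthly dose, so one case is informative. That explains why hypersensitivity has a one-subject criterion. It does not explain why a death already judged related should lack one.

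A reader might also want a one-subject trigger for ischemic cardiovascular events, a named AESI (section 10.6.1: "AESIs for this study include the potential risks of ischemic cardiovascular events, infusion reactions and hypersensitivity, and neurologic sequelae associated with bone overgrowth"). The documents do not support calling its absence a flaw. Section 11.5 singles out cardiovascular events for DMC review. Exclusion 11 removes subjects with prior infarction, angina, ischemic stroke or TIA, and item 11a leaves other risk factors to clinical judgment. A single non-fatal ischemic event in an open-label, single-arm study is hard to attribute, so whether to notify on one is a trade-off for the sponsor.

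**Conclusion.** The point holds for related deaths not due to hypersensitivity. As written, 8.3.3 gives the most severe grade a higher notification threshold than a survivable Grade 4 hypersensitivity reaction, and no visible passage requires event-driven DMC notice of a first related death. This follows from the wording alone.

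The size is modest. With 112 subjects, an assumed 0.25% risk of such a death and 0.5% to 2% for other qualifying events, the chance that a related death occurs and is the first qualifying event is about 0.10 to 0.19. Those numbers restate the rule under assumed rates and are not evidence of harm. How quickly the DMC would learn of the death depends on the charter and cannot be judged here.

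Severity is minor: a low-cost safety improvement. Both criteria lead only to DMC review, and the finding is an inverted threshold within one section.

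**What to change.** Extend the one-subject criterion in section 8.3.3 to any Grade 5 event assessed as related by the Investigator or the sponsor. State that this means notification only, with no automatic pause. Keep the two-subject criterion for all other related serious events of Grade 3 or higher. Align the DMC charter; if it already has such a trigger, a cross-reference in 8.3.3 is enough.

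The cost is one sentence in the protocol, a matching line in the charter, and at most an occasional extra ad hoc DMC review: about 0.28 expected over the study with 112 subjects at the assumed 0.25% risk.

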8.4. Informed Consent

Informed consent must be obtained from the patient at the Screening visit, prior to entry into the Observation period and prior to performing any study-related procedures. In the event that a subject is rescreened, a new informed consent form (ICF) must be signed unless it has been < 30 days since the previous ICF signature was obtained.

8.5. Screening Requirements

There are 2 screening visits: the Screening Visit to determine eligibility for entry into the Observation Period of the study and the Retreatment Screening Visit to confirm eligibility to enter the Retreatment Period of the study in order to receive retreatment with setrusumab. All screening evaluations specified in Table 3 must be completed and reviewed to confirm eligibility for study entry (initial Screening Visit into the Observational /period) and Retreatment Period entry (Retreatment Screening Visit). The Investigator will maintain a screening log to record details of all subjects screened and to confirm eligibility or record reasons for screening failure, as applicable.

At the Screening Visit, informed consent will be obtained, general medical information (ie, demographics, general medical history, and concomitant medications) will be collected.

During the Retreatment Screening Visit subjects are rescreened and safety laboratory tests are run to ensure subject safety prior to retreatment with setrusumab (Section 8.2). Calcium levels assessed at the Retreatment Screening Visit must be in the normal range prior to the Retreatment Visit. While receiving treatment with setrusumab, subjects can receive a daily dose of mg calcium as background treatment or maintain a higher dose if they are already receiving a higher dose. If the subject's calcium level is not within the normal range, decision to retest should be made in conjunction with the Medical Monitor. 25-OH-vitamin D should be mol/L prior to setrusumab retreatment. If the subject's 25-OH-vitamin D is of mol/L at the Retreatment Screening Visit, the subject should be treated as per the local guidelines and retested during the study to maintain levels above mol/L.

9. INTERVENTION(S)

Table 9: Study Interventions

IV, intravenous; CCI

Intervention	Setrusumab
Dose Formulation	mg lyophilized powder for solution
Unit Dose Strength(s)/Dosage Level(s)	20 to 40 mg/kg QM CC
Route of Administration	60-minute IV infusion
Use	Experimental

The dosing strategy in the Retreatment and Extension Periods will be based on the pharmacokinetic (PK) and serum bone turnover data from the Phase 2b ASTEROID study and the Phase 2 Period of the UX143-CL301 study. The selected dose will be in the range of 20 to 40 mg/kg

9.1. Investigational Product: Setrusumab

Setrusumab is supplied as a mg powder in a vial for solution for infusion. The vial is filled with excess setrusumab (ie, mg) to ensure that the full dose is removed from the vial once reconstituted. Setrusumab is manufactured, packaged and labelled according to current Good Manufacturing Practices.

Additional information on physical and chemical properties of setrusumab are provided in the IB. **Preparation and Administration**

For detailed preparation and administration information refer to Pharmacy Manual.

QM, once a month.

Setrusumab mg powder for solution for infusion needs to be reconstituted with sterile water for injection diluted in % dextrose in a mL IV bag to be administered over CCI Setrusumab will be administered at scheduled study visits as outlined in the Schedule of Events (Table 3).

9.1.2. Clinical Observation and Supportive Care

Subjects will be monitored for any infusion reactions that may occur during or immediately following drug administration. Infusion-related reactions are an AESI (Section 10.6.1) and will be reported accordingly (Table 11). For the first 2 administrations of study drug per patient, oral or tympanic temperature, blood pressure, respiratory rate and pulse will be monitored at the beginning of the infusion at CCI after the end of the infusion. For the remaining infusions, vital signs will be monitored during the infusion.

9.2. Prior and Concomitant Therapy

Subjects may receive concomitant medications as required, with the exception of those identified in Section 9.3 as prohibited. Concomitant medications will be recorded as described in Section 10.6.7.

Study site personnel should indicate on relevant laboratory request documents if the subject is taking high dose biotin supplements (found in multivitamins, biotin supplements, and some supplements to support hair, skin and nail growth) due to potential risk of assay interference (eg, troponin) (FDA, 2019).

9.3. Restricted or Prohibited Medications, Devices, and Procedures

Certain medications and procedures are prohibited per the exclusion criteria in Section 8.2, including:

- Concurrent participation in any study that is examining the safety and efficacy of any investigational product or investigational medical device that alters bone health during the Retreatment and Extension Periods, per discretion of the Investigator in consultation with the Medical Monitor
- Willing to discontinue bisphosphonate use at least 3 months prior to the Retreatment Screening Visit (if applicable).

9.4. Treatment Compliance

Study drug will be administered at the study site via a single IV infusion by qualified personnel. The dose, start time, stop time, and volume of infusion will be recorded in the subject's case report form (CRF).

9.5. Treatment Assignment

9.5.1. Treatment Assignment

This is an open-label study. No study drug is provided during the Observation Period. During the Retreatment Period, all subjects will receive the same dose of setrusumab administered QM. During the Extension Period, subjects will be randomized 1:1 to either continue treatment with open-label setrusumab QM or transition to open-label setrusumab CCI. For the Extension Period dosing groups, randomization will be stratified by OI type (I vs III/IV). Randomization will be completed using interactive response technology (IRT).

10. ASSESSMENTS

Assessments, including sample collection, and associated timing are provided in Table 3 and Table 4. Protocol waivers or exemptions are not allowed.

Data will continue to be collected for all endpoints on all subjects, including those who have discontinued study treatment but remain in the study. Site Investigators will be trained about the importance of subject retention and steps to prevent missing data. Reasons for missed assessments will be collected.

The completeness of the data affects the integrity and accuracy of the study analyses. Therefore, every effort will be made to ensure complete, accurate and timely data collection, and to avoid missing data.

10.1. Skeletal Assessments

10.1.1. Dual-energy X-ray Absorptiometry

Bone mineral density of the lumbar spine, total hip, femoral neck, distal 1/3 radius, and whole body minus head will be evaluated by DXA at time points specified in Table 3.

As noted in Section 10.6.2, DXA scans will also be collected retrospectively as a part of medical history. Calcium tablets should not be taken 2 hours prior to a DXA lumbar scan. Additional details regarding DXA are provided in the Study Imaging Manual.

[figure not shown]
10.1.2. Radiography

A skeletal survey and vertebral radiographs will be performed at time points specified in Table 3. Additional radiographs may be performed to confirm a reported fracture event. As noted in Section 10.6.2, radiographs for fracture events occurring prior to study entry will be collected via chart review as a part of medical history.

Radiographs of the left hand will be analyzed and evaluated for bone age and metacarpal thickness. Lateral spine radiographs will be assessed for morphometric vertebral fractures based on vertebral height using the semi-quantitative Genant method and 6-point quantitative morphometric method; Spine Deformity Index, kyphosis, and lordosis will be evaluated. Anterior-posterior spine radiographs will be used to evaluate the degree of scoliosis. Fracture healing will also be assessed.

[figure not shown]
Fractures reported via diary (Section 10.2.4) may be radiographed at the next scheduled visit (unless radiographs are obtained prior to the visit). An effort will be made to secure radiographs taken between study visits at other institutions.

All radiographs will be assessed for the presence of fractures by central readers, who are blind to the subject's treatment and trained for consistent evaluation. Additional details regarding radiography are in the Study Imaging Manual.

